**Table 3 Initial Dose of Roxadustat**

epoetin† (IU/week)	darbapoetin alfa† (µg/week)	roxadustat (mg/dose) TIW
<8,000	<40	100
8,000 to 16,000	40-80	150‡
>16,000	>80	200§

† Average prescribed weekly dose in the last 4 weeks prior to randomization.

‡ If the initial dose of 150 mg exceeds the maximum dose of 3.0 mg/kg, then 100 mg is to be used as the starting dose.

§ If the initial dose of 200 mg exceeds the maximum dose of 3.0 mg/kg, then 150 mg is to be used as the starting dose.

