**Table 2: Initial Dose of Roxadustat**

epoetin† (IU/week)	darbepoetin alfa† (µg/week)	roxadustat (mg/dose) TIW
<8,000	<40	100
8,000 to 16,000	40-80	150‡
>16,000	>80	200§

TIW: 3 times weekly

† Average prescribed weekly dose in the last 4 weeks prior to randomization.

‡ If the initial dose of 150 mg exceeds the maximum dose of 3.0 mg/kg, then 100 mg is to be used as the starting dose.

§ If the initial dose of 200 mg exceeds the maximum dose of 3.0 mg/kg, then 150 mg is to be used as the starting dose.

After randomization, roxadustat will be dosed TIW for the entire duration of the treatment period. The dose of roxadustat will remain constant during the first 4 weeks of the treatment period. After week 4, dose adjustments are permitted on a 4-weekly interval and will be aimed at keeping subjects' Hb levels between 10.0 to 12.0 g/dL. Dose adjustments will be based upon current Hb and change in Hb over the preceding 4 weeks as illustrated in Table 3 (deviation from the 4-week period is allowed anytime during the study in case of excessive hematopoiesis or Hb  $\geq$ 13.0 g/dL).

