## Maximum dose for roxadustat

The maximum allowed roxadustat dose in this study is set at 3.0 mg/kg (based on postdialysis weight in HD subjects and weight minus abdominal fluid based on last filling in PD subjects) or 400 mg per administration, whichever is lower. The highest dose tested in healthy subjects is 5 mg/kg single dose and 3.75 mg/kg TIW. The doses were safe and well tolerated with transient dose dependent heart rate increases observed. No maximum tolerated dose was reached in the clinical development of roxadustat based on the observed pharmaco-dynamic response (plasma EPO levels) and the predicted relation between EPO levels and Hb response; therefore exploration of higher doses was not deemed necessary. Plasma EPO levels increased in a supra-linear manner with increasing roxadustat doses. It is expected that the majority of the subjects will show adequate Hb response at substantially lower doses than the maximum allowed dose.

The treatment period of 104 weeks will provide sufficient data on the efficacy and safety of long term treatment of anemia with roxadustat in ESRD subjects on stable dialysis.

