#### **3.2 Inclusion Criteria**

Subject is eligible for the study if all of the following apply:

1. Institutional Review Board (IRB)-/Independent Ethics Committee (IEC)-approved written informed consent and privacy language as per national regulations has been obtained from the subject or legally authorized representative prior to any study-related procedures (including withdrawal of prohibited medication, if applicable).
2. Subject age is  $\geq 18$  years.
3. Subject is on stable HD, HDF or PD treatment with the same mode of dialysis for  $\geq 4$  months prior to randomization.
4. For subject receiving hemodialysis, the vascular access must be via native arteriovenous (AV) fistula or graft, or permanent, tunneled catheter.
5. Subject is on IV or SC epoetin (i.e. epoetin alfa, beta, theta, zeta, delta or omega) or IV or SC darbepoetin alfa treatment for  $\geq 8$  weeks prior to randomization with stable weekly doses ( $\leq 30\%$  change from the maximum prescribed average weekly dose, i.e.  $([\max - \min] / \max \leq 0.3)$ ) during 4 weeks prior to randomization. Subjects on polyethylene glycol-epoetin beta (Mircera®) are not to be included.
6. Mean of the subject's 3 most recent Hb values, as measured by central laboratory, during the screening period, obtained at least 4 days apart, must be  $\geq 9.5$  g/dL and  $\leq 12.0$  g/dL with an absolute difference  $\leq 1.3$  g/dL between the highest and the lowest value. The last Hb value must be within 10 days prior to the randomization visit (day 1).
7. Subject has a ferritin level  $\geq 100$  ng/mL ( $\geq 220$  pmol/L) at screening.
8. Subject has a transferrin saturation (TSAT) level  $\geq 20\%$  at screening.
9. Subject has a serum folate level  $\geq$  lower limit of normal (LLN) at screening.
10. Subject has a serum vitamin B12 level  $\geq$  LLN at screening.

11. Subject's alanine aminotransferase (ALT) and aspartate aminotransferase (AST) are  $\leq 3$  x upper limit of normal (ULN), and total bilirubin (TBL) is  $\leq 1.5$  x ULN.
12. Subject's body weight (postdialysis weight) is 45.0 kg to a maximum of 160.0 kg.
13. Female subject is either:  
Of non-childbearing potential:
  - postmenopausal (defined as at least 1 year without any menses) prior to screening,
  - or documented surgically sterile.Or if of childbearing potential:
  - agree not to try to become pregnant during the study and for 28 days after the final study drug administration.

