**Table 4 Dose Adjustment Rules for Roxadustat**

Change in Hb Over Past 4 Weeks (g/dL) a	Hb (g/dL)		
	<10.5	10.5 to <12.0	12.0 to <13.0
< -1.0	↑	↑	No change
-1.0 to 1.0	↑	No change	↓
> 1.0	No change	↓	↓

Hb: hemoglobin

a Subtract first Hb value from last value Hb to calculate the change

- All dose adjustments are made based on Hb values using HemoCue®, a point-of-care device.
- Dose increases by 1 dose step (↑) and reductions by 1 dose step (↓) are pre-set

- If the dose adjustment is ‘No change’ per the above table, the dose remains unchanged and the next dose adjustment review is 4 weeks after that visit.
- The dose steps for roxadustat are as follows: 20, 40, 50, 70, 100, 150, 200, 250, 300, and 400 mg.
- The maximum dose is the dose step corresponding to 3.0 mg/kg (based on postdialysis weight in HD subjects and in PD subjects weight minus abdominal fluid based on last filling) per administration or 400 mg, whichever is lower. At study visits where weight is collected the default weight and maximum allowed dose step for a subject will be adjusted if the weight change is  $\geq 5\%$  compared to the previous default weight collected in the study. Initial default weight is weight at randomization visit.
- If there is a safety concern, investigators may deviate from the dose adjustment rules for roxadustat. This should be discussed with the medical monitor and documented in the source documentation.
- Contact the medical monitor if dose adjustments would lead to doses outside the limits of the dose step range; i.e. lower than 20 mg or higher than 400 mg.

In the following cases dose adjustment may be made at any time outside the 4-weekly interval:

- Dose reduction in case of excessive hematopoiesis
- Dose increase by 1 step in case subject Hb  $< 9.0$  g/dL (HemoCue®) and no dose adjustment occurred in the preceding 4 weeks.

At any time when Hb  $\geq 13.0$  g/dL

- Stop dosing
- Resume dosing when Hb  $< 12.0$  g/dL at a dose that is reduced by 2 steps
- Next dose adjustment review is 4 weeks after dose resumption and in 4-weekly intervals thereafter.

Dose Adjustment for Excessive Hematopoiesis

At any time during the Treatment Period:

- If Hb increases by  $>2.0$  g/dL at any time within 4 weeks, the dose should be reduced by 1 dose step

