6.5.4 Variables related to study drugs

Randomization/Treatment Arms

[Table 11](#) below presents the groups to which subjects are randomized.

Table 11 Treatment arms

Randomization Arm Code (ARMCD)	Randomization Arm (ARM)
A	Roxadustat - TIW
B	ESA (Darbepoetin Alfa or Epoetin Alfa)

Analysis date of First Dose Intake

Date of first study drug dose intake is collected in the Day 1 visit in the Randomization eCRF. In case of a missing/partial date, the earliest available date will be used. It will be on the same day than the randomization date and before the next dose date.

Analysis Date of Last Dose

Date of Last Study Drug Dose is collected at the End of Treatment visit in the End of Treatment eCRF. When this date is not known, all efforts should be made to obtain the date from the investigator. If it is still missing after all efforts have been made, then the visit date of the End of Treatment Visit will be used as the Analysis Date of Last Dose. If subject is lost to follow-up and none of these dates are available, then the date of the last available assessment during the study will be used.

Duration of exposure in days

For each subject, the Length of Time on treatment will be calculated in days, using the following formula:

(‘Analysis Date of Last Dose’ - ‘Analysis Date first dose intake’) + 1

Amount of Prescribed (planned) Medication

Roxadustat

The number of milligrams prescribed at each visit (including unscheduled visits) is captured in the *Changes in Dosing* eCRF. The investigator reported dose and frequency will be used when available. For first administration, the IRS reported dose and frequency will be used.

The prescribed weekly dose at each visit (including unscheduled visits) will be calculated as prescribed dose x 3 as the prescribed frequency is TIW for roxadustat.

Each visit will have an associated start and end date as follows:

- Each visit (including unscheduled) will have an associated start date,
- Each visit (including unscheduled) will have an associated end date. This date will be the date of the next consecutive visit [including unscheduled visits and EOT] minus 1 day.

Time periods of interest are defined below (monthly is defined as a period of 4 weeks or 28 days) as follows:

Time Period	Analysis Start Day	Analysis End Day*
Week 4 (Month 1)	Day 1	Day 28
Week 8 (Month 2)	Day 29	Day 56
Week 12 (Month 3)	Day 57	Day 84
Week 16 (Month 4)	Day 85	Day 112
Week 20 (Month 5)	Day 113	Day 140
Etc....		

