Table 12 Information Fraction (IF) and One Sided Significance Level (alpha) for the Primary Endpoint

Information Fraction (IF)	alpha (1-sided)
0.5	0.0147
0.6	0.0154
0.7	0.0162
0.8	0.0174
0.9	0.0191
0.97	0.0216

Following the parametric chain procedure, if at least one of the two null hypotheses is rejected at the significance level of 0.0174, the other one can be tested at a significance level of 0.025 while still controlling the overall type I error. The study will be successful for the EU primary efficacy endpoint if either of the null hypotheses is rejected, i.e., if the lower limit of the two-sided $100*(1-\alpha*2)\%$ CI for the difference in least square means from the MMRM model is greater than -0.75g/dL.

If both null hypotheses are rejected, secondary endpoints will be assessed on the overall population. Otherwise, secondary endpoints will not be formally tested.

The covariates will be:

- Previous ESA treatment (epoetin versus darbepoetin alfa);
- Region (region A versus region B);
- History of cardiovascular, cerebrovascular or thromboembolic diseases (Yes versus No)[#];
- Average prescribed weekly ESA dose prior to randomization (≤ 200 IU/kg epoetin or ≤ 1 μ g/kg darbepoetin alfa versus > 200 IU/kg epoetin or > 1 μ g/kg darbepoetin alfa)^{*};
- Baseline Hb value (Continuous).

[#]: This covariate is derived according to a list of cardiovascular disease preferred terms received from the study physician after softlock.

^{*}: For the analyses, the average prescribed weekly ESA dose prior to randomization will be taken from the screening procedure form, in the eCRF. Upon review of data, this covariate was excluded from analysis as number of subjects in the high dose group was too low for the variable to be meaningful.

For these covariates, the IRS value used at randomization will be compared to the eCRF value.

In case of stratification errors during the randomization process, the analysis will use the correct covariates as recorded on the eCRF for the subject.

MMRM model:

An MMRM model will be run for the purpose of implicit imputation of missing data by using all the available information from the observed data via the within-patient correlation

structure. The analysis will be based on the estimated difference between the two treatment arms overall mean effects throughout the evaluation period (weeks 28 to 36) based on this MMRM model.

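### The starting-dose rule for the top prior-ESA tier puts roxadustat subjects of 45.0 to <50.0 kg at 150 mg, above the study's own 3.0 mg/kg maximum; few or no subjects may be affected

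*Protocol*

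**What the plan says.** Protocol Section 2.2.2, Table 3, sets the first roxadustat dose from the average prescribed weekly ESA dose over the last 4 weeks. The tiers are 100 mg (epoetin below 8,000 IU/week or darbepoetin below 40 µg/week), 150 mg (8,000 to 16,000 IU or 40 to 80 µg) and 200 mg (above 16,000 IU or above 80 µg).

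Two footnotes adjust for weight:
- ‡, marked on the 150 mg entry: "If the initial dose of 150 mg exceeds the maximum dose of 3.0 mg/kg, then 100 mg is to be used as the starting dose".
- §, marked on the 200 mg entry: "If the initial dose of 200 mg exceeds the maximum dose of 3.0 mg/kg, then 150 mg is to be used as the starting dose".

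Both the protocol synopsis (Table 2) and SAP Section 3.2.3 (Table 3) carry the same table and footnotes.

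The cap is stated generally in Section 2.2.2: "The maximum allowed roxadustat dose in this study is set at 3.0 mg/kg", or 400 mg per administration if that is lower. Section 5.1.2.1 (Table 4) repeats it and lists the steps: "The dose steps for roxadustat are as follows: 20, 40, 50, 70, 100, 150, 200, 250, 300, and 400 mg". The eligible weight range is in Section 3.2, criterion 12: "Subject's body weight (postdialysis weight) is 45.0 kg to a maximum of 160.0 kg".

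**The concern.** Both footnotes exist to keep the first dose within 3.0 mg/kg. Footnote § tests 200 mg against the cap, moves the subject to 150 mg and stops, without testing 150 mg. At the low end of the eligible weight range 150 mg is still too much, and ‡ shows that the authors knew this for the middle tier. A site that follows § exceeds the stated maximum, and a site that follows the maximum departs from §. Receiving an incorrect dose is a notifiable deviation (PD3, protocol Section 8.1.6), so the correct starting dose has to be unambiguous.

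The starting dose also persists. The synopsis says: "The dose of roxadustat will remain constant during the first 4 weeks of the treatment period". The exceptions are Hb of 13.0 g/dL or more, excessive hematopoiesis, or an investigator's deviation for a safety concern. Section 1.2.2 reports completed CKD studies only up to 3.0 mg/kg, and Section 1.2.2.1 reports higher exposure in dialysis subjects than in healthy subjects.

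**Working it through.** No published figure has to be reproduced here. The check applies the table to the eligible weights.

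**Inputs.** Cap 3.0 mg/kg (Section 2.2.2); weight 45.0 to 160.0 kg (Section 3.2); starting doses and fallbacks (Table 3); dose steps (Table 4).

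**Step 1: weight below which each dose exceeds the cap (dose ÷ 3.0).**
- 200 ÷ 3.0 = 66.7 kg
- 150 ÷ 3.0 = 50.0 kg
- 100 ÷ 3.0 = 33.3 kg, below the minimum eligible weight

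A top-tier subject under 66.7 kg falls to 150 mg by §. If that subject is also under 50.0 kg, 150 mg exceeds the cap.

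**Step 2: size of the excess.**

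| Weight (kg) | Cap = 3.0 × weight (mg) | 150 mg as mg/kg | 100 mg as mg/kg |
|---|---|---|---|
| 45.0 | 135 | 3.33 | 2.22 |
| 49.9 | 149.7 | 3.01 | 2.00 |
| 50.0 | 150 | 3.00 (within cap) | 2.00 |

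The largest excess is 150 − 135 = 15 mg, and 15 ÷ 135 = 11%.

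**Step 3: all tiers and weights.** Table 3 with its footnotes was applied at every weight from 45.0 to 160.0 kg in 0.1 kg steps. The only breaches are in the top tier at 45.0 to 49.9 kg. The low and middle tiers never breach.

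**Step 4: comparison with ‡ and with titration.** With a 45.0 kg minimum, ‡ can only ever act on the band 45.0 to <50.0 kg, because that is where 150 mg exceeds the cap. In that band ‡ rejects 150 mg and § assigns it. With the cap at 135 to 149.7 mg, the highest listed step within it is 100 mg. Footnote § therefore starts these subjects one step above the highest dose that titration would allow.

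**Step 5: who could be affected.** The tier boundary divided by weight gives the minimum prior ESA dose:
- epoetin: 16,000 ÷ 50 = 320 and 16,000 ÷ 45 = 356 IU/kg/week
- darbepoetin: 80 ÷ 50 = 1.60 and 80 ÷ 45 = 1.78 µg/kg/week

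All such subjects lie inside the stratum above 200 IU/kg or 1 µg/kg. SAP Section 7.4.1.1.1 drops that stratum as a covariate because the "number of subjects in the high dose group was too low for the variable to be meaningful". No count is given.

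**Step 6: after the fix.** With the order 200 mg, else 150 mg, else 100 mg, no weight from 45.0 to 160.0 kg exceeds 3.0 mg/kg in any tier. The affected band starts at 2.00 to 2.22 mg/kg.

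**The case against.** The strongest reply is that the general maximum already governs. It is not limited to titration, it stands in the same section as Table 3, and Section 5.1.2.1 takes the initial default weight from the randomization visit, so the cap applies from day 1. A careful reader could also apply the condition in ‡ to any starting dose that has become 150 mg. On that reading § is incomplete drafting and nobody is dosed above the cap. This is a plausible account of the intent, but it is not written. No text says which rule prevails, ‡ is marked only on the middle tier, and § read alone gives 150 mg.

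Second, the actual dose came from the IRS, and its specification is not in the documents. SAP Section 6.5.4 confirms the source: "For first administration, the IRS reported dose and frequency will be used". This stands: the documents cannot show whether any above-cap dose was issued.

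Third, the clinical weight is limited. The highest dose reached, 3.33 mg/kg, is below the 3.75 mg/kg three times weekly that Section 2.2.2 reports as safe and well tolerated in healthy subjects, and dosing stops or falls on high or fast-rising Hb. This also stands, qualified by the higher exposure in dialysis subjects.

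Fourth, timing. Protocol version 3.0 is dated 30 May 2017, with a planned study end in 3Q2018, and SAP version 3.0 is dated 10 September 2018 and refers to work after soft lock. A change of wording in that SAP is unlikely to alter anyone's starting dose. This limits what the wording change can achieve but does not make the rule correct.

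**Conclusion.** The point holds. As written, footnote § assigns 150 mg to top-tier roxadustat subjects of 45.0 to <50.0 kg. That is 3.01 to 3.33 mg/kg against a maximum of 3.0 mg/kg, an excess of at most 15 mg or 11%. The conclusion rests only on figures in the protocol and on reading § as it stands, with no unstated rule that the cap overrides it.

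The consequences are narrow. The affected group is very small and may be empty, and whether any subject received such a dose is unknown. Sample size, alpha and the primary analysis are untouched. It should still be corrected, because a stated dosing rule contradicts the protocol's own maximum and the correction is simple.

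**What to change.** Extend footnote § in protocol Table 3, synopsis Table 2 and SAP Table 3 with: *and if 150 mg also exceeds 3.0 mg/kg, then 100 mg is to be used*. This matches ‡ at the same weight.

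Confirm from the IRS specification which dose it assigned in this band, and list any subject whose first dose exceeded 3.0 mg/kg. SAP Section 6.5.4 already converts prescribed dose to mg/kg using day 1 weight. For hemodialysis subjects the listing should also show the third-screening-visit weight, which protocol Section 5.4.4 says is entered in the IRS for day 1. If enrolment is complete, the listing is the part that still has value.

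The cost is one clause in three places, one system check and one listing. As a dosing change, the clause would go through the amendment process in protocol Section 8.3.3. No analysis changes. The clinical trade-off is a lower start for a few subjects with a high ESA requirement. For them 100 mg is also the top step within the cap while they remain under 50.0 kg, so the existing provisions for IV iron and rescue ESA at the maximum dose would apply, subject to their other criteria, if the response is inadequate.

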## Dose adjustments for roxadustat

Dose adjustment of roxadustat will be aimed at keeping subjects' Hb levels between 10.0 to 12.0 g/dL and will be based upon current Hb (assessed with the HemoCue® point-of-care device at the investigational site) and change in Hb over the preceding 4 weeks.

More details on dose adjustments are described in Section [5.1.2.1](#)

## Maximum dose for roxadustat

The maximum allowed roxadustat dose in this study is set at 3.0 mg/kg (based on postdialysis weight in HD subjects and weight minus abdominal fluid based on last filling in PD subjects) or 400 mg per administration, whichever is lower. The highest dose tested in healthy subjects is 5 mg/kg single dose and 3.75 mg/kg TIW. The doses were safe and well tolerated with transient dose dependent heart rate increases observed. No maximum tolerated dose was reached in the clinical development of roxadustat based on the observed pharmaco-dynamic response (plasma EPO levels) and the predicted relation between EPO levels and Hb response; therefore exploration of higher doses was not deemed necessary. Plasma EPO levels increased in a supra-linear manner with increasing roxadustat doses. It is expected that the majority of the subjects will show adequate Hb response at substantially lower doses than the maximum allowed dose.

The treatment period of 104 weeks will provide sufficient data on the efficacy and safety of long term treatment of anemia with roxadustat in ESRD subjects on stable dialysis.

## 2.3 Endpoints

All statistical analyses are performed using the Central Laboratory data.

### 2.3.1 Primary Endpoint

There are 2 separate regionally based primary efficacy endpoints in this study, depending upon whether the data are being filed to support submission to the US FDA or to Ex-US health authorities, such as the EMA.

- The EU (EMA) primary efficacy endpoint is change in Hb from BL to the average level during the evaluation period (defined as week 28 until week 36), without having received rescue therapy (i.e. RBC transfusion for all subjects or ESA for subjects treated with roxadustat) within 6 weeks prior to and during this 8-week evaluation period.
- The US (FDA) primary efficacy endpoint is change in Hb from BL to the average level during the evaluation period (defined as week 28 until week 52), regardless of rescue therapy.

### 2.3.2 Key Secondary Endpoints

The secondary efficacy endpoints in this study are:

- Hb response, defined as mean Hb during weeks 28 to 36 within the target range of 10.0 to 12.0 g/dL without having received rescue therapy within 6 weeks prior to and during this 8-week evaluation period.

- Change from BL in Low Density Lipoprotein (LDL) cholesterol to the average LDL cholesterol of weeks 12 to 28.
- Mean monthly IV iron use (mg) during day 1 to week 36 (monthly defined as a period of 4 weeks).
- Change from BL in SF-36 Physical Functioning (PF) sub-score to the average PF sub-score of weeks 12 to 28.
- Change from BL in SF-36 Vitality (VT) sub-score to the average VT sub-score of weeks 12 to 28.
- Blood pressure effect
  - Change from BL in mean arterial pressure (MAP) to the average MAP value of weeks 20 to 28.
  - Time to an increase in blood pressure: An increase from BL of  $\geq 20$  mm Hg systolic blood pressure (SBP) and  $SBP \geq 170$  mmHg or an increase from baseline of  $\geq 15$  mmHg diastolic blood pressure (DBP) and  $DBP \geq 100$  mmHg during weeks 1 to 36.

